7.2 Secondary objectives

- Identify clinical and/or biochemical factors associated with an optimal ($\geq 60\%$) CD34+ CE
- Confirm data, from the published literature, regarding the correlation between Ht and CD34+ CE in a cohort of subjects largely composed by hematological patients.
- Develop a prediction model for optimal ($\geq 60\%$) CD34+ CE using pre-LP clinical and/or biochemical factors.

8. Methods

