8.1.1 Primary Endpoint

Impact, measured by statistical correlation, of clinical (age, sex, type of donor, diagnosis, recent RBC transfusion) and biochemical (pre-LP values of Ht, Hb, WBC and PLT) variables on CD34+ CE.

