8.1.2 Secondary Endpoints

- Correlation of clinical (age, sex, type of donor, diagnosis, recent RBC transfusion) and biochemical variables (pre-LP values of Ht, Hb, WBC and PLT) with an adequate ($\geq 60\%$) CD34+ CE.
- Correlation of pre-LP Ht levels and recent (≤ 60 days) RBC transfusion with CD34+ CE, especially in the autologous setting.
- AUROC (Area Under the ROC Curve) of a pre-LP model based on clinical parameters aimed at predicting an adequate ($\geq 60\%$) CD34+ CE.

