8.5 Sample Size

Total study population: 113 subjects of which 74 hematological/non hematological patients and 39 stem cell donors.

The number of subjects evaluated is determined by the clinical activity of the Apheresis Unit (SC Medicina Trasfusionale) and has been considered adequate considering the number of subjects included in other similar study present in the literature^{7,8}. Due to descriptive nature of the analysis planned, no pre-analysis sample size was determined.

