8.7 Statistical Analysis

For descriptive analyses, quantitative variables will be expressed as mean and standard deviation or as median, interquartile range (IQR) and minimum-maximum range, while categorical variables will be expressed as absolute and relative frequencies.

Aiming to evaluate the impact of clinical and biochemical variables on CD34+ CE, we will examine the association between CD34+ CE and age, sex, type of donor (patients vs healthy donors), hematocrit, hemoglobin level, WBC counts, platelets count.

Analysis will be performed by fitting data in generalized linear models for continuous variables and logistic regression for binary variables. In order to avoid overfitting, the selection of variables to be included in multivariable models will be performed by Backward stepwise regression. All models will be adjusted for significant clinical confounders.

Statistical analysis will be performed using the JMP Pro 16.0 Statistical Analysis Software (SAS Institute, Cary, NC). P values <0.05 (two tailed) were considered statistically significant.

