8.7.2 Secondary Endpoint: Analysis

The association of biological variables with adequate CD34+ CE will be evaluated using linear logistic model of regression and strength of correlation was assessed evaluating Odds Ratio values. Accuracy of clinical prediction model for optimal CD34+ CE will be evaluated by estimating AUROC.

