8.9 Study Limits

We will try to correct two possible bias within our cohorts:

- by excluding patients affected by Acute Lymphoblastic Leukemia who underwent apheresis procedure in order to collect a salvage CD34+ autologous backup. Those patients are characterized by abnormally high pre-LP CD34+ counts due to disease immunophenotype (often CD34+) and low bone marrow disease burden. Moreover the practice of collecting an autologous CD34+ backup in case of allogeneic engraftment failure or disease relapse, although not detrimental for patients, it's not supported by strong practicing evidence.
- By considering only the first apheresis procedure for each patients in order to avoid any possible selective bias.

The main limits of this study could be:

- the small cohort dimension which do not allow significant evaluations about influence of underlying disease, mobilization regimens and poor mobilizing condition.
- the retrospective nature of data which do not allow to clearly assess influence and utility of RBC transfusion pre-LP.

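### The secondary prediction model for CE ≥60% is judged by AUROC alone, which cannot show whether its predicted probabilities are too extreme; at this sample size that is likely, though not certain

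*Combined protocol and SAP*

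**What the plan says.** Section 7.2 lists as its third secondary objective: "Develop a prediction model for optimal" CE (≥60%), from pre-apheresis factors. The matching endpoint in section 8.1.2 is "AUROC (Area Under the ROC Curve) of a pre-LP model based on clinical parameters aimed at predicting an adequate" CE, and section 8.7.2 gives the whole of its analysis: "Accuracy of clinical prediction model for optimal CD34+ CE will be evaluated by estimating AUROC".

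The modelling method comes from section 8.7: "Analysis will be performed by fitting data in generalized linear models for continuous variables and logistic regression for binary variables". The one stated protection against an overfitted model is there too: "In order to avoid overfitting, the selection of variables to be included in multivariable models will be performed by Backward stepwise regression".

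The data are small. Section 8.5 gives "Total study population: 113 subjects of which 74 hematological/non hematological patients and 39 stem cell donors", and section 8.9 limits the analysis to one procedure per subject ("By considering only the first apheresis procedure for each patients").

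No section mentions a calibration slope, intercept or plot, a Brier score, penalised estimation, bootstrap or cross-validation, or a validation sample. Section 8.7.4 (supplemental analysis) is marked not applicable. Section 8.9 admits that the cohort is small but does not connect this to the prediction model.

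**The concern.** A logistic prediction model produces a probability. Two questions decide whether it is accurate: does it rank subjects correctly (discrimination), and does a predicted 85% come true in about 85% of such subjects (calibration)? AUROC answers only the first.

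When variables are selected and fitted by unpenalised logistic regression on about a hundred subjects, the retained coefficients tend to be too large. High predictions are then too high and low ones too low. The plan has no step that would show this and none that would reduce it, yet it treats AUROC as the measure of accuracy. A model with a respectable AUROC could therefore be published with a formula that overstates how sure one can be of reaching 60% CE in a given subject.

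This is separate from optimism in the AUROC. An AUROC corrected for optimism would still be a rank statistic.

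**Working it through.** The plan states no expected AUROC and no calculated sample size, so there is no figure to reproduce. The subject count adds up: 74 + 39 = 113.

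**Inputs from the documents**
- Observations: at most 113 (sections 8.5 and 8.9).
- Candidates: section 8.7 names seven (age, sex, donor type, hematocrit, hemoglobin, WBC, platelets). Section 8.1.1 lists nine: "clinical (age, sex, type of donor, diagnosis, recent RBC transfusion) and biochemical (pre-LP values of Ht, Hb, WBC and PLT) variables". With two indicators for the three diagnosis groups of section 8.3, nine variables become 9 − 1 + 2 = 10 parameters.
- Two-sided 0.05 (section 8.7). It is used below as the threshold for staying in the model, because the plan gives no separate one.

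**Step 1: AUROC ignores the scale of the predictions.** AUROC is the probability that a randomly chosen subject with CE ≥60% has a higher linear predictor than one without. Multiplying the linear predictor by any s > 0 leaves the order, and so the AUROC, unchanged. The calibration slope becomes 1/s. A check on 200,000 simulated subjects with a correct model (s = 1), stretched about its mean:

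| s | 1/s | AUROC | Calibration slope | Predictions below 0.1 or above 0.9 |
|---|---|---|---|---|
| 1 | 1.00 | 0.730 | 1.00 | 3% |
| 1.5 | 0.67 | 0.730 | 0.67 | 14% |
| 2 | 0.50 | 0.730 | 0.50 | 26% |
| 3 | 0.33 | 0.730 | 0.33 | 44% |

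This step needs no assumption about the study.

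**Step 2: the planned procedure at n = 113, hematocrit the only true predictor.** Assumptions that are not in the documents: CE = 60 + b(Ht − 36.1) + normal error with SD 13; b = 0.8 (Ht–CE correlation about 0.35, weaker) or 1.2 (about 0.49, stronger); half the subjects at CE ≥60%. Models come from backward logistic selection at P<0.05 and are tested on new subjects. Repeating this with differing assumed covariate distributions and similar effect sizes gave these ranges of the median slope:

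| Candidates | Weaker Ht effect | Stronger Ht effect |
|---|---|---|
| 7 variables | 0.72–0.75 | 0.83–0.89 |
| 10 parameters | 0.64–0.71 | 0.79–0.87 |

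Single datasets spread widely. In one ten-parameter run the interquartile ranges were 0.51–0.94 (weaker) and 0.69–1.07 (stronger).

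**Step 3: several true predictors.** Assumptions: three true predictors, 9 or 12 candidate parameters, 30% to 70% of subjects at CE ≥60%, 600 repetitions per scenario. With a true AUROC of about 0.73, the median apparent AUROC was 0.74–0.76 and the median slope in new subjects 0.64–0.75. Apparent AUROC of at least 0.70 together with a slope below 0.8 occurred in 56%–67% of the fitted models. With 9 candidates and half the subjects at CE ≥60%, a true AUROC of 0.81 gave a median slope of 0.78 and 55%; a true AUROC of 0.66 gave 0.58 and 39%. Repetitions in which no variable was retained (up to 12%) are left out.

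**Step 4: what such slopes mean.** Take a prediction of 85% from a model that is correct at 50%. Its logit is ln(0.85/0.15) = 1.735.
- Slope 0.70: 0.70 × 1.735 = 1.214, a true probability of 77%.
- Slope 0.85: 0.85 × 1.735 = 1.474, a true probability of 81%.

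The ten-parameter run with the quoted interquartile ranges agrees. Subjects predicted above 80% averaged 84% predicted against 75% observed (weaker effect), and 86% against 82% (stronger effect).

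**Step 5: checking on the same data would not help.** Maximum likelihood sets Σ(y − p) = 0 and Σx(y − p) = 0 for each retained x, hence Σ(linear predictor)(y − p) = 0. These are the equations that a recalibration model solves at intercept 0 and slope 1. The apparent slope is therefore 1 however overfitted the model is.

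**The case against.** The strongest defence has four parts.

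*AUROC is the declared endpoint, and no probabilities are promised.* This is fair. No section says that individual probabilities will be issued or used for decisions, and the introduction speaks of a possible hematocrit threshold, for which discrimination is directly relevant. But section 7.2 commits the study to developing a prediction model, and section 8.7.2 calls its AUROC accuracy. It is reasonable to ask for calibration, though not to assume clinical use.

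*Backward selection already guards against overfitting.* The slopes above were obtained with that selection in place, and their medians remain below 1.

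*The size depends on assumptions.* This stands. The documents give no CE distribution, no hematocrit spread, no share at CE ≥60% and no numerical correlation. The candidate list is also unsettled: seven variables in section 8.7, nine in section 8.1.1, and clinical parameters only in the wording of section 8.1.2. The short list gives milder slopes. With a weaker effect, selection kept no variable in about 8% of runs, which leaves no model to miscalibrate.

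*The extreme predictions concern few subjects.* This also stands. About 5% (weaker) to 10% (stronger) of subjects were predicted above 80%: 0.05 × 113 ≈ 6 to 0.10 × 113 ≈ 11.

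A reader might infer that following the plan must yield over-extreme coefficients. The documents do not support that: the spread of slopes reaches 1 or nearly so. Nor is it a fault of AUROC that it corrects nothing, since no performance measure does. The gap is that the plan has neither a calibration measure nor a shrinkage step.

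**Conclusion.** The point holds as a cheap improvement to the third secondary objective. That AUROC is the only planned performance measure, and that it cannot reveal over-extreme probabilities, follows from the text and from the definition of AUROC. That such probabilities will arise is likely, not certain. The median calibration slope in new subjects is about 0.65 to 0.75 for a weaker hematocrit effect and 0.8 to 0.9 for a stronger one, conditional on the assumed covariates, effect sizes, share at CE ≥60% and 0.05 selection threshold.

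Two wider inferences are not supported. The primary analysis, which relates factors to CE as a continuous quantity, is unaffected. And harm to individual subjects would require that the probabilities, or a cut-off on them, be used in practice, which the documents do not plan.

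**What to change.** In section 8.7.2, define accuracy of the prediction model as discrimination and calibration, and add:

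1. Fix the candidate list, the coding of diagnosis and the selection threshold.
2. Bootstrap the whole modelling process, repeating the backward selection in every resample. State how resamples that retain no variable are handled, and report how many there are.
3. Apply each resample's model to the original data. Report the mean slope as the optimism-corrected calibration slope, with its spread, beside the optimism-corrected AUROC from the same resamples.
4. If probabilities or a scoring formula are published, multiply the coefficients by the bootstrap slope and re-estimate the intercept. Ridge-penalised logistic regression is an acceptable alternative.
5. Otherwise state that the model is exploratory and that its probabilities are not for individual use.

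The cost is a few lines of text and some analysis time; no new data are needed. The probabilities will move towards the average and look less decisive. The shrinkage factor is itself imprecise at this sample size: in simulation it brought the median slope to 0.95–1.05 with a slightly lower mean Brier score, but it helped in only about 60% of datasets. The uncertainty of the slope should therefore be reported with it.

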8.7.3 Ad interim analysis

NA.

8.7.4 Supplemental analysis

NA

8.8 Quality Control

Dipartimento Area dei Servizi
SC Medicina Trasfusionale

Direttore: [name]

Tel. Segreteria Direzione: [name]

E-mail: [contact]; [contact]

Each procedure proposed to the patients and performed will strictly adhere to current clinical practice and recommendations. All data attain current clinical practice.

As promoter, Fondazione IRCCS Ca' Granda, Ospedale Maggiore Policlinico could apply a quality control to the study. In this case, the PI must allow the monitor to verify directly to all the study documents and to spend a portion of his/her time and staff to discuss the monitoring results and other aspects of the study. Moreover, the Regulatory Authorities can perform inspections. In this case, the PI must allow the authorities to directly verify all the documents related to the study and spend a portion of his/her time and staff to allow the inspector to discuss the monitoring and eventually other aspects of the study

8.9 Study Limits

We will try to correct two possible bias within our cohorts:

- by excluding patients affected by Acute Lymphoblastic Leukemia who underwent apheresis procedure in order to collect a salvage CD34+ autologous backup. Those patients are characterized by abnormally high pre-LP CD34+ counts due to disease immunophenotype (often CD34+) and low bone marrow disease burden. Moreover the practice of collecting an autologous CD34+ backup in case of allogeneic engraftment failure or disease relapse, although not detrimental for patients, it's not supported by strong practicing evidence.
- By considering only the first apheresis procedure for each patients in order to avoid any possible selective bias.

The main limits of this study could be:

- the small cohort dimension which do not allow significant evaluations about influence of underlying disease, mobilization regimens and poor mobilizing condition.
- the retrospective nature of data which do not allow to clearly assess influence and utility of RBC transfusion pre-LP.

8.10 Other aspects

NA

9 Subjects protection

This study will be conducted by Good Clinical Practice (GCP) rules; in accordance with the ethical principles that have their origin in the Declaration of Helsinki and with the respect to the European clinical practice, in compliance with all international guidelines and national law regulation in Italy.

Dipartimento Area dei Servizi
SC Medicina Trasfusionale

Direttore: [name]

Tel. Segreteria Direzione: [name]

E-mail: [contact]; [contact]

The protocol must be submitted to the Independent Ethics Committee (IEC) for review and will receive IEC approval/favourable opinion before initiation of the study. During the study, any amendments to the protocol must also be approved by IEC.

9.1 Informative note to the subject and consent form for processing of personal data

Being the Policlinico Institute, promoter of the study, an IRCCS (Istituto di Ricovero e Cura a Carattere Scientifico- health and research institute), in compliance with current legislation on the protection and protection of personal data (EU Reg. 679/2016) and Legislative Decree 196/2003 (Code of Privacy) as amended by Legislative Decree 101/2018, for the data collected and processed by the Promoter and by the other participating centers having the same IRCCS nature, it will not be mandatory to ask the study participants for consent to the use of their personal data for the conduct of the study itself.

In compliance with the provisions of art. 110 bis paragraph IV of the amended Legislative Decree 196/2003, due to the instrumental nature that the health care activity assumes with respect to research at Scientific Hospitalization and Treatment Institutes, the treatment, for research purposes, of personal data already collected during standard clinical activity, including the anonymization of the data itself, does not in fact constitute further processing.

